6.10.2. Secondary Efficacy Endpoint Analysis

Secondary efficacy endpoint analyses will be based on the FAS.

The secondary efficacy endpoints of this study include:

- Changes from baseline in scores of MDS-UPDRS Part III (motor examination) in subjects after 1, 4, 8 weeks of treatment. Evaluation time point at each visit: ≥ 12 hours from the most recent dose of anti-PD drug;
- Changes from baseline in scores of MDS-UPDRS Part III (motor examination) in subjects after 1, 4, 8, 12 weeks of treatment. Evaluation time point at each visit: 2 ± 1 hours from the most recent

dose of anti-PD drug;

- Changes from baseline in scores of MDS-UPDRS Part I, II and IV in subjects after 1, 4, 8 and 12 weeks of treatment;
- Changes from baseline in the total scores of MDS-UPDRS in subjects after 1, 4, 8, 12 weeks of treatment, including:
 - Total score 1: II+III; wherein, the evaluation time point for MDS-UPDRS Part III (motor examination) is ≥ 12 hours from the most recent dose of anti-PD drug;
 - Total score 2: II+III; wherein, the evaluation time point for MDS-UPDRS Part III (motor examination) is 2 ± 1 hours from the most recent dose of anti-PD drug;
 - Total score 3: I+II+III; wherein, the evaluation time point for MDS-UPDRS Part III (motor examination) is ≥ 12 hours from the most recent dose of anti-PD drug;
 - Total score 4: I+II+III; wherein, the evaluation time point for MDS-UPDRS Part III (motor examination) is 2 ± 1 hours from the most recent dose of anti-PD drug;
 - Total score 5: I+II+III+IV; wherein, the evaluation time point for MDS-UPDRS Part III (motor examination) is ≥ 12 hours from the most recent dose of anti-PD drug;
 - Total score 6: I+II+III+IV; wherein, the evaluation time point for MDS-UPDRS Part III (motor examination) is 2 ± 1 hours from the most recent dose of anti-PD drug.

The analysis of secondary efficacy endpoints will be summarized using the same statistical methods as described in Section [6.10.1.1](#) for the primary analysis. Based on the model, the least squares means (LSM) of the change from baseline in MDS-UPDRS-related scores at each endpoint visit, along with their 95% CIs, will be derived. Additionally, the between-group differences in LSM, their two-sided 95% CIs, and nominal P-values will be calculated.

Additionally, line graphs will be plotted to display the least squares mean changes from baseline in MDS-UPDRS Part III (Motor Examination) scores at each visit (assessed at ≥ 12 hours and 2 ± 1 hours after the last dose of anti-PD medication), along with their corresponding 95% CIs.

The MDS-UPDRS Part III (Motor Examination) scores at each visit (assessed at ≥ 12 hours and 2 ± 1 hours after the last dose of anti-PD medication) will be plotted as line graphs showing the arithmetic mean change from baseline and its standard error.

6.11. Exploratory Analysis

Exploratory analyses will be performed based on the FAS.

6.11.1. Exploratory Analysis of Inflammatory Markers

The exploratory inflammatory endpoints are the changes in inflammatory markers from baseline at 4, 8, and 12 weeks of treatment. The exploratory inflammatory biomarkers in this trial include: interleukin (IL)-1 β , IL-2, IL-4, IL-5, IL-6, IL-8, IL-10, IL-12p70, IL-17A, interferon (IFN)- α , IFN- γ , and tumor necrosis factor (TNF)- α . The specific testing indicators should be determined based on the actual

implementation at each center. Descriptive statistics will be performed for inflammatory marker results at each visit and their changes from baseline.

Exploratory inflammatory endpoints will be analyzed using analysis of variance (ANOVA) or nonparametric tests: if the variables followed a normal distribution, ANOVA will be used for between-visit group comparisons; otherwise, the Wilcoxon rank-sum test will be employed for between-visit group comparisons.

List the inflammatory indicators of the subjects.

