A Mixed Model for Repeated Measures (MMRM) will be used to calculate nominal P values for between-group comparisons of primary and secondary endpoints; where applicable, analysis of covariance (ANCOVA) will be employed to calculate nominal P values for between-group comparisons of primary endpoints. For exploratory endpoints with normally distributed variables, analysis of variance (ANOVA) will be used to calculate nominal P-values for between-group comparisons; otherwise, the Wilcoxon rank-sum test will be employed for between-group comparisons to calculate nominal P-values.

Confidence Interval (CI)

Unless otherwise specified, the CI refers to a two-sided 95% CI, with one more decimal place than the derived data or parameters.

P-value

This study does not conduct formal hypothesis testing, and the summarized P-values will be nominal P-values. P-values should be retained to 4 decimal places. If the P-value is less than 0.0001, it should be presented as "<.0001"; if the P-value will be greater than 0.9999, it should be presented as ">.9999".

Treatment Group

Unless otherwise specified, it will be summarized by the TJ0113 capsules 200 mg group, TJ0113 capsules 400 mg group, and the placebo group.

Study Day 1

Study Day 1 is defined as the day of the first dose of the investigational product. All safety and efficacy assessments will be calculated based on Study Day 1.

- If the visit date \geq the first dose date, then: Study day = Visit date - First dose date + 1
- If the visit date $<$ the first dose date, then: Study day = Visit date - First dose date.

There is no definition of Study Day 0 in this study.

Repeated Measurements or Assessments

If more than one measurement or assessment of a certain parameter is conducted at the same time point during the same visit according to the study protocol, it will be defined as a repeated measurement or assessment. The mean value of repeated measurements or evaluations will be used as the analytical value. In this study, all 12-lead electrocardiogram (ECG) parameters will be measured twice, and clinical evaluations will be performed with duplicate assessments.

Baseline Value

Unless otherwise specified, baseline is defined as the last valid measurement or assessment result prior to the first dose (including scheduled or unscheduled visits). If an unscheduled visit date coincides with the scheduled visit date and the exact time is unknown, the results from the scheduled visit should be used as the baseline.

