6.10.1.1. Primary Analysis

The analysis will be performed using a mixed models for repeated measures (MMRM) with the changes from baseline in the MDS-UPDRS Part III scores after 12 weeks of treatment as the dependent variable, whether subjects have been receiving levodopa, the background medication for PD (yes vs. no) at a stable dose at baseline and the baseline MDS-UPDRS Part III score as the covariates, and the treatment group, visit, and the treatment group-by-visit interaction as the fixed effects. The covariance matrix prioritizes an unstructured (UN) covariance matrix. If the results do not converge, the following covariance structures will be tested sequentially: heterogeneous Toeplitz (TOEP), first-order autoregressive (AR1), and compound symmetry (CS). The first covariance structure that achieves convergence will be used. Based on the model, calculate the least squares mean of the change from baseline in MDS-UPDRS Part III score at 12 weeks of treatment, along with its 95% CI, the between-group difference in least squares means with its two-sided 95% CI, and the nominal P-value.

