6.10.1.2. Sensitivity Analysis Methods

The sensitivity analysis of the primary endpoint will be conducted based on the FAS.

Sensitivity Analysis 1: For missing data in the primary endpoint, a Last Observation Carried Forward (LOCF) imputation will be applied, followed by a sensitivity analysis using Analysis of Covariance (ANCOVA). The imputation rules are detailed in Section [6.2.1](#). The model used the change from

baseline in the MDS-UPDRS Part III score at 12 weeks of treatment as the dependent variable, with baseline stable use of levodopa as anti-PD background medication (yes vs. no), baseline MDS-UPDRS Part III score, and treatment group as covariates. Based on the model, calculate the least squares mean of the change from baseline in MDS-UPDRS Part III score at 12 weeks of treatment, along with its 95% CI, the between-group difference in least squares means with its two-sided 95% CI, and the nominal P-value. The reference procedure is as follows:

```
ODS OUTPUT lsmeanc1=lsmeans lsmeandiffcl=lsmeansdiff;
```

```
PROC GLM data=dataset;
```

```
  CLASS trtpn pd;
```

```
  MODEL chg = trtpn pd base/SOLUTION;
```

```
  LSMEANS trtpn/CL STDERR PDIFF COV;
```

```
run;
```

Sensitivity Analysis 2: Assuming the missing data mechanism is missing at random (MAR), a sensitivity analysis will be conducted using the same method as the primary analysis after performing multiple imputation for missing values. For imputation rules, refer to Section [11.1](#) of the SAP Appendix.

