6.11.2. Exploratory PD Biomarker Analysis

The exploratory PD biomarker endpoints are the changes from baseline in α -synuclein and GFAP after 12 weeks of treatment. Descriptive statistics will be performed on the results of α -synuclein and GFAP indicators at 12 weeks post-treatment and their percentage changes from baseline.

Analyze α -synuclein and GFAP using analysis of variance (ANOVA) or nonparametric tests: if the variables follow a normal distribution, employ ANOVA for between-visit group comparisons; otherwise, use the Wilcoxon rank-sum test for between-visit group comparisons.

List the PD biomarker indicators for subjects.

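### Free improvement, low priority: the exploratory changes from baseline are tested without the baseline value or the levodopa stratum as covariates, which is unbiased but less precise than it could be

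*SAP*

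**What the plan says.** SAP 6.1 sets the general rule: "For exploratory endpoints with normally distributed variables, analysis of variance (ANOVA) will be used to calculate nominal P-values for between-group comparisons", with the Wilcoxon rank-sum test otherwise. SAP 6.11.1 repeats it for the inflammatory markers: "if the variables followed a normal distribution, ANOVA will be used for between-visit group comparisons; otherwise, the Wilcoxon rank-sum test will be employed". SAP 6.11.2 begins "The exploratory PD biomarker endpoints are the changes from baseline in" alpha-synuclein and GFAP, and then says "if the variables follow a normal distribution, employ ANOVA for between-visit group comparisons". SAP 6.11.3 gives the same rule for ASMI, grip strength and 6-metre walking speed. Protocol 11.4.5 is the source: analysis of variance or nonparametric tests, with details left to the SAP. None of these sections names a covariate, and none plans a confidence interval for the group difference.

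The other efficacy models do adjust. The primary MMRM (SAP 6.10.1.1) takes levodopa use "at a stable dose at baseline and the baseline MDS-UPDRS Part III score as the covariates". Its ANCOVA sensitivity analysis (SAP 6.10.1.2) uses levodopa use, "baseline MDS-UPDRS Part III score, and treatment group as covariates". For the rest, SAP 6.10.2 says "The analysis of secondary efficacy endpoints will be summarized using the same statistical methods as described in Section" 6.10.1.1.

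Randomisation is stratified by stable levodopa use (Protocol 5.3.1). All the exploratory measures are scheduled at V2, before the first dose (Protocol 8.3.1 to 8.3.3). On inference, SAP 6.1 states: "This study does not conduct formal hypothesis testing, and the summarized P-values will be nominal P-values".

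**The concern.** The baseline is subtracted to form the change score but is not a term in the model, and the randomisation stratum is not used at all. A simple change score fixes the slope of follow-up on baseline at 1. If the true slope is lower, baseline noise is carried into the comparison and could have been removed. Leaving out a stratum that was balanced by design can also make the reported standard error too large.

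What is at stake is precision in the trial's only biomarker and muscle read-outs. About 50 subjects per group are planned, with no formal sample-size basis (SAP section 4). Each centre decides which inflammatory markers and muscle tests it performs, so some endpoints may have fewer.

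**Working it through.** **Inputs from the documents.** 150 subjects split 1:1 into cohorts gives 75 per cohort. Split 2:1, that is 50 active and 25 placebo, so 50/50/50 overall, as stated. The plan gives no power, SD or effect size for these endpoints, so there is no figure of its own to reproduce.

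**Assumed inputs.** The correlation rho between baseline and follow-up is taken as 0.3, 0.5, 0.7 and 0.9, with equal SD s at both visits. The stratum effect on the change is 0 or 0.5 SD. None of these is in the documents.

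**Precision, closed form.**
- Change score, unadjusted: variance = 2s²(1 − rho).
- ANCOVA residual: variance = s²(1 − rho²).
- ANCOVA-to-ANOVA variance ratio: (1 + rho)/2, so the SE ratio is sqrt((1 + rho)/2).
- Without equal SDs (s0 at baseline, s1 at follow-up), the unadjusted variance exceeds the adjusted one by (s0 − rho·s1)². This is never negative, so adjustment costs nothing beyond the degrees of freedom.

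In the table, the fourth column is 50 divided by the variance ratio. The last column is power with ANCOVA when the effect is set so that the unadjusted comparison has 80% power (a reference point, not a figure in the plan; two-sided 0.05, 50 per arm).

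| rho | Variance ratio | SE ratio | ANOVA n per arm matching 50 by ANCOVA | Power, from 80% |
|---|---|---|---|---|
| 0.3 | 0.65 | 0.806 | 76.9 | 93.5% |
| 0.5 | 0.75 | 0.866 | 66.7 | 89.9% |
| 0.7 | 0.85 | 0.922 | 58.8 | 86.0% |
| 0.9 | 0.95 | 0.975 | 52.6 | 82.0% |

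**Validity, by simulation.** One dose against placebo, 50 per arm, a two-level stratum split 25/25 in each arm, 4,000 trials per setting.
- Bias of the unadjusted difference: at most 0.006 SD.
- Type I error with no stratum effect: 4.8% to 5.3% (ANOVA) and 4.6% to 5.1% (Wilcoxon).
- Type I error with a 0.5 SD stratum effect: 2.2% to 4.5% (ANOVA) and 2.3% to 4.3% (Wilcoxon), lowest at rho 0.9. A repeat run gave 2.6% to 4.8%.
- Type I error of the adjusted analysis: 4.4% to 5.5%.
- Simulated SE ratio: 0.80–0.81, 0.86–0.87, 0.92–0.94 and about 0.98 at the four values of rho, in line with the formula.

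**Why the unadjusted tests become conservative.** A balanced stratum adds nothing to the true variance of the group difference, but it does enter the residual variance. With a 50:50 stratum and a 0.5 SD effect it adds 0.5²/4 = 0.0625 (in units of s²). At rho 0.9 the change variance is 2(1 − 0.9) = 0.2, so the reported SE is too large by sqrt(0.2625/0.2) = 1.15. At rho 0.3 the change variance is 1.4 and the factor is sqrt(1.4625/1.4) = 1.02. That is why the effect is marked at high rho and slight at low rho. Including the stratum mainly corrects the reported SE; the simulated SE ratios barely differ with and without a stratum effect.

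**Power at a fixed effect of 0.5 SD, no stratum effect,** at rho 0.3/0.5/0.7/0.9: ANOVA 55/70/89/100%, Wilcoxon 53/68/87/100%, ANCOVA 73/81/93/100%.

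**The case against.** The strongest reply is that this is a preference. The endpoints are exploratory, the P-values are nominal, the SAP follows Protocol 11.4.5, and no conclusion of the trial depends on power here. Every magnitude above rests on an assumed correlation, and at rho 0.9 baseline adjustment shortens the SE by only 2.5%. The benefit of the levodopa term cannot be computed from the documents. All of this stands. It sets the priority, but does not remove the gain from data that will already be in hand.

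A reader might infer stronger claims, which the documents do not support:

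- *The SAP contradicts itself, or the tests are wrong.* SAP 6.1 assigns ANCOVA to the primary endpoint and ANOVA to the exploratory ones, so the difference is a stated choice. The missing covariates cause neither bias nor inflated type I error.
- *The exploratory tests are sound in every respect.* The check covers only the missing covariates. How a two-sample rank-sum test is applied to three groups, and how normality is judged, are separate matters.
- *A log scale, a site term for locally assayed markers, or a rule for values below the assay limit is also required.* These are separate options that rest on assumed marker distributions and laboratory differences. The primary and secondary models have no site term either.
- *SAP 6.11.2 expressly tests change, with percentage change descriptive only.* The endpoint is defined as change and percentage change appears under descriptive statistics, but the sentence on testing does not name its variable. The reading is plausible, not stated.

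**Conclusion.** The point holds as an efficiency improvement of low priority. The exploratory comparisons leave out two covariates that the trial collects and uses in its other efficacy models. With equal variances at the two visits, adding the baseline multiplies the SE by 0.81 to 0.975 for rho from 0.3 to 0.9, whatever the group size (degrees of freedom aside). The benefit is therefore real for variable markers and small for measures that hardly move in 12 weeks. Adding the stratum matters only if levodopa use predicts the change; at an assumed 0.5 SD effect and exact balance, the unadjusted tests run at about 2% to 5% instead of 5%. The genomic association endpoint has no stated test and is outside this point.

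**What to change.** In SAP 6.1 and 6.11.1 to 6.11.3, make the main exploratory analysis an ANCOVA of change from baseline. Its terms are three-level treatment (200 mg, 400 mg, placebo), the baseline of the same measure, and levodopa stratum (yes/no). Report each dose against placebo with a two-sided 95% CI and nominal P-value. For clearly non-normal markers, use the same model on a transformed or rank scale. Keep the planned ANOVA and Wilcoxon tests as a sensitivity analysis. Record the change from Protocol 11.4.5 in SAP section 8, which at present lists no changes, and settle it before unblinding so that the covariates cannot look data-driven.

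The cost is SAP text, code and two degrees of freedom (from 147 to 145 residual with 150 subjects and three groups). It is free in the sense that it needs no new data and loses no subjects, because a change score already requires the baseline. A site term, a mandated log scale and a below-limit rule may be considered separately; this change does not depend on them.

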6.11.2. Exploratory PD Biomarker Analysis

The exploratory PD biomarker endpoints are the changes from baseline in α -synuclein and GFAP after 12 weeks of treatment. Descriptive statistics will be performed on the results of α -synuclein and GFAP indicators at 12 weeks post-treatment and their percentage changes from baseline.

Analyze α -synuclein and GFAP using analysis of variance (ANOVA) or nonparametric tests: if the variables follow a normal distribution, employ ANOVA for between-visit group comparisons; otherwise, use the Wilcoxon rank-sum test for between-visit group comparisons.

List the PD biomarker indicators for subjects.

6.11.3. Exploratory Analysis of Skeletal Muscle Mass and Function Assessment

Exploratory endpoints for skeletal muscle mass and function assessment include:

- Change in ASMI from baseline measured by dual-energy X-ray absorptiometry (DXA) after 12 weeks of treatment.
- Changes from baseline in muscle strength (grip strength) after 12 weeks of treatment;
- Changes from baseline in 6-meter walking speed test after 12 weeks of treatment.

The specific testing indicators should be determined based on the actual implementation at each center. Descriptive statistics will be performed on the results of skeletal muscle mass and functional assessment indicators after 12 weeks of treatment, as well as their changes from baseline.

Analysis of ASMI, muscle strength (grip strength), and 6-meter walk speed test will be performed using analysis of variance (ANOVA) or nonparametric tests: if the variables followed a normal distribution, ANOVA will be used for inter-visit group comparisons; otherwise, the Wilcoxon rank-sum test will be employed for inter-visit group comparisons.

List the indicators for assessing skeletal muscle mass and function in subjects.

6.12. Safety Analysis

Safety endpoints include: AEs, laboratory tests, vital signs, physical examinations, and 12-lead ECG. Safety analyses will be based on the SS.

6.12.1. Drug Exposure

Based on SS, analyze and tabulate drug exposure in subjects. A descriptive summary of the total actual drug exposure (mg), total exposure duration (days), and actual dose level (mg/day) for the subjects will be provided. For specific definitions and calculation methods, please refer to Section [6.2.2](#).

6.12.2. AEs

Adverse events will be coded using the Medical Dictionary for Regulatory Activities (MedDRA) version 27.0 or higher. The severity of AEs will be classified according to the National Cancer Institute (NCI) Common Terminology Criteria for Adverse Events (CTCAE) version 5.0.

Summarize and tabulate adverse events, with the summary including only TEAEs and the tabulation encompassing all AEs.

The summary table of adverse events will include the number of AE occurrences, the number and percentage of subjects. When calculating the incidence of adverse events, multiple occurrences will be counted if the same subject experiences different adverse events multiple times. When calculating the number of subjects with adverse events, each subject will be counted only once, even if they experience multiple different adverse events. The percentage of adverse events will be calculated based on the number of subjects who experienced adverse events, not the number of adverse event occurrences. When counting the severity of adverse events, if the same subject experiences multiple adverse events under the same SOC or PT, the number of instances will be counted multiple times, while the number of cases will be only counted for the most severe occurrence.

The overall summary table of AEs will include the following TEAE categories:

- All TEAEs
- All TRAEs
- Treatment-emergent SAEs
- Treatment-emergent drug-related SAEs
- CTCAE \geq Grade 3 TEAE
- CTCAE \geq Grade 3 TRAE
- TEAE leading to death
- TEAE leading to dose suspension
- TEAEs leading to dose reduction
- TEAE leading to dose discontinuation
- TEAEs leading to early withdrawal

Summarize the above TEAE categories by SOC and PT. All TEAEs and SAEs during treatment will also be summarized by SOC, PT, and the highest CTCAE grade.

List all adverse events in detail.

Statistical Analysis Plan Version 1.0

Summarize the number and percentage of deceased subjects, along with the causes of death. List the causes of death.

6.12.3. Laboratory Tests

Descriptive statistics will be performed for the results of hematology, blood biochemistry, coagulation function, and Ccr measurements at each visit, as well as their changes from baseline.

For the clinical significance assessment of hematology, blood biochemistry, urinalysis, and coagulation function, cross-tabulation will be used to summarize the changes in subjects' clinical assessment categories from baseline to the worst post-baseline clinical assessment category (clinically significant abnormality > abnormality without clinical significance > normal > not examined). Analyze the "urine white blood cells" and "urine sediment microscopic white blood cells" results in the clinical significance of urinalysis collectively, and analyze the "urine red blood cells" and "urine sediment microscopic red blood cells" results collectively.

List the hematology, blood biochemistry, urinalysis, coagulation function, and Ccr of the subjects. Tabulate all abnormal test results.

For laboratory tests, if the original result contains an equal sign(e.g., \leq , \geq), the numeric value will be directly used. If the original result contains only a less-than symbol, subtract 0.0001 from the numeric value. If the original result contains only a greater-than symbol, add 0.0001 to the numeric value.

